7.4.1.2 Sensitivity Analysis

In order to assess the robustness of findings from the primary efficacy analysis, the following sensitivity analyses will be performed:

- ACR20-CRP response at Week 12/ET using LOCF for components and NRI for response (see Section 7.11.2. for details, no multiplicity adjustment)
- ACR20-CRP response at Week 12/ET using LOCF for components and the PPS as analysis set

Note: The FAS will be replaced with the PPS as analysis set, to assess robustness results from FAS. Multiplicity adjustment will be done.

- ACR20-CRP response at Week 12/ET using Observed data (data as collected, no imputation, no multiplicity adjustment)
- ACR20-CRP response at Week 12/ET using multiple imputation, assuming missing at random mechanism (see Section 7.11.2. for details)
- ACR20-CRP response at Week 12/ET using placebo Multiple Imputation (pMI) (see Section 7.11.2. for details)
- Re-randomization test

In order to assess the validity of dynamic allocation, re-randomization test will be conducted, using Monte Carlo sampling in the following equation.

$$\hat{p} = \frac{1 + \sum_{m=1}^M I(|S_m - \bar{S}| \geq |S_{obs} - \bar{S}|)}{M + 1}, \bar{S} = \sum_{m=1}^M \frac{S_m}{M}$$

I: indicator function

\hat{p} : two – sided Monte Carlo p value

S_{obs} : observed test statistics

S_m : test statistics sampling from permutation distribution

M: the number of Monte Carlo sampling

Based on the equation above, the two-sided Monte Carlo \hat{p} will be calculated by following steps.

1. The entry order of subjects, the 3 allocation factors (sites, prior biologic-DMARD-IR, concomitant DMARD at Baseline use, and study region), and ACR20-CRP response at Week 12/ET are fixed. Then, simulate dynamic allocation which is actually conducted in RAJ3, and continue to all subjects. The random seed is 1001.
2. When getting 1st simulation result, for the ACR20-CRP response at Week 12/ET, the same analysis described in 7.4.1.1 will be conducted using logistic regression model with data getting from step 1, and calculate Z test statistics for 150 mg versus placebo, 100 mg versus placebo.

Z test statistics are defined as follows.

$$Z = \frac{\hat{\beta}_1}{SE(\hat{\beta}_1)}$$

$\hat{\beta}_1$: Maximum likelihood estimate value of β_1

3. Repeat the simulation process (Step 1 and 2) up to M times (set as 9999). During individual simulations, if quasi-complete separation, or complete separation occurs, then these results will not be included in the 9999 simulation results, and these result will be replaced with the next results which does not occur quasi-complete separation, nor complete separation. Note that the random seed is used from 1000 + m at mth simulation.
 4. When completing M (set as 9999) simulation results, then the two-sided Monte Carlo \hat{p} will be calculated.
- Sensitivity Analysis of ACR20-CRP response at Week 12/ET using LOCF for components to assess the impact of HAQ-DI caused by inappropriate description in the local questionnaire in Taiwan
 Note: In the local questionnaire used in Taiwan (i.e. written in Taiwanese), there was one inappropriate description about "aids or devices" checkbox in Hygiene category in place of "Bathtub bar" (Refer to Section 10.5 Appendix 5). To examine the impact of this inappropriate description, sensitivity analysis of primary analysis will be conducted on the following assumptions.

b	Checked "Bathtub bar" at Baseline	Checked "Bathtub bar" at Weeks 4, 8, 12 and Week 12/ET
1		
2		
3		

* The Checkbox "Bathtub bar" taken with the inadequate description was inactivated (not checked) including the all data up to Week 12 for all subjects in Taiwan and inactivated (not checked data) Checkbox "Bathtub bar" will be used in the primary analysis (Section 7.4.1.1).

7.4.1.3 Interaction Analysis

Interaction Analysis will be performed in two steps as follows:

Step 1. Logistic regression model (Section 7.4.1.1) including interactions of [the prior biologic-DMARD-IR x treatment group interaction], [concomitant DMARD at Baseline use x treatment group interaction] and [study region x treatment group interaction], separately, will be conducted in order to present the information of significance of interactions.

The interaction term will be assessed at a two-sided significance level of 0.05.

Step 2. If the interaction term described above is significant, odds ratio and the other statistics based on the model including interactions will be evaluated.

7.4.1.4 Subgroup Analysis

In order to evaluate homogeneity of treatment effects across subjects with different demographic and baseline characteristics, subgroup analysis of the primary efficacy variables

will be performed, respectively. In addition, logistic regression model described in Section 7.4.1.1 will be performed for each subgroup category and odds ratios, and 95% confidence intervals will be provided for each subgroup. The subgroups in Section 7.8 will be analyzed. As for subgroup analysis, it is not executed any statistical testing. These subgroup analyses will be displayed graphically as Dot-and-Forest plot.

7.4.1.5 Adjustment for imbalances in demographics and other baseline characteristics

As for the variables in which imbalance is present in 7.2.2, adjusted analysis will be performed to evaluate the influence. Logistic model with the variables in which imbalance is present as a covariate added to logistic regression model (Section 7.4.1.1) will be performed.

7.4.1.6 Time to the first response analysis

Time to the first ACR20-CRP response analysis will be analyzed as following procedure. This analysis will be applied during first 12 weeks of treatment period, because placebo treated subjects are switched to ASP015K after Week 12.

- Time to the first response analysis will be analyzed using KM profile plots for each treatment group (including reference group), and stratified log-rank test will be used for comparing each ASP015K dose group time-to-event profile versus placebo. Stratified analyses will use the following 3 stratification factors: the prior biologic-DMARD-IR, concomitant DMARD at Baseline use, and study region (Japan, Korea, and Taiwan). This analysis will be applied up to Week 12.
- For each subject, time to the first event (days) will be defined as the number of days from the date of initial dose of study drug or reference drug to the date the first occurrence of the event, and calculated as: date of the first occurrence of the event (most recent assessment among each components if the assessment date is different among each components) – date of initial dose of study drug or reference drug +1. In addition to this, Cox proportional hazards model with a main effect for treatment group (Placebo, ASP015K 100 mg, and ASP015K 150 mg) and the prior biologic-DMARD-IR, concomitant DMARD at Baseline use, and study region (Japan, Korea, and Taiwan) as the covariates will be used comparing each ASP015K dose group versus placebo (except for reference group).
- Subjects who complete the treatment period through Week 12 without having the event will be censored at one day before the dosing at Week 12 day up to Day 92, and the censored time will be calculated as: one day before the dosing at Week 12 day up to Day 92 – date of initial dose of study drug or reference drug +1.
- In the time to response analysis, each subject will be classified as either a responder (event = 1 in time-to-event model) or a non-responder (event = 0 in time-to-event model), based on the definition in Section 6.1.1. The definition of event is the same as the definition of the binary response.

- Subjects who prematurely discontinued the treatment period through Week 12 (i.e. before the dosing at Week 12) without having the event up to Day 92 will be censored at the date of early discontinuation, and the censored time will be calculated as: date of early discontinuation from the treatment period up to Day 92 – date of initial dose of study drug or reference drug +1.

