In the Japanese clinical trial in RA patients (015K-CL-RAJ1), the incidence rates of AEs in the ASP015K 25 mg, 50 mg, 100 mg, and 150 mg groups were 70.9%, 64.9%, 52.7%, and 67.2%, respectively. These rates were comparable with that of the placebo group (64.3%). The incidence rates of AEs whose relationship to the study drug could not be ruled out for the ASP015K 25 mg, 50 mg, 100 mg, and 150 mg groups were 38.2%, 43.9%, 29.1%, and 55.2%, respectively. These rates were higher than that reported for the placebo group (28.6%). By severity (NCI-CTCAE), most were either Grade 1 or Grade 2. In the placebo and ASP015K 25 mg, 50 mg, 100 mg, and 150 mg groups, the numbers of subjects with serious adverse events (SAEs) were 1 (1.8%), 1 (1.8%), 2 (3.5%), 3 (5.5%), and 0, respectively. Death was reported from 1 subject of the 50 mg group (cerebral haemorrhage). AEs resulted in treatment discontinuation in 10 (17.9%), 7 (12.7%), 5 (8.8%), 6 (10.9%), and 4 (6.9%) subjects of the placebo, ASP015K 25 mg, 50 mg, 100 mg, and 150 mg groups, respectively. The most common reason was rheumatoid arthritis aggravated (21/32).

- CONFIDENTIAL -

Rheumatoid arthritis, nasopharyngitis, blood creatine phosphokinase (CPK) increased, diarrhoea, cystitis, constipation, stomatitis, dyspepsia, lipids increased, and blood triglycerides increased were reported at $\geq 5\%$ incidence rates from 1 or more groups. By the MedDRA System Organ Class (SOC), Infections and infestations, Gastrointestinal disorders, Musculoskeletal and connective tissue disorders, and Investigations showed high incidence rates. Blood creatine phosphokinase increased were observed in 0, 2 (3.6%), 1 (1.8%), 1 (1.8%), and 7 (12.1%) subjects of the placebo, ASP015K 25 mg, 50 mg, 100 mg, and 150 mg groups, respectively. Most cases were transient, and all subjects except 1 who prematurely discontinued the study recovered or were recovering. With regard to clinical laboratory testing, compared with the placebo group, the ASP015K groups showed decreased levels of neutrophils, platelets, and estimated glomerular filtration rate (eGFR) and elevated levels of CPK, hemoglobin, lymphocytes, creatinine, total cholesterol, LDL, HDL, and triglycerides. No noteworthy changes were detected in vital signs or ECG recordings.

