5 TREATMENTS AND EVALUATION

5.1 Dosing and Administration of Study Drugs or Reference Drugs and Other Medications

5.1.1 Dose/Dose Regimen and Administration Period

(1) Dose and administration period

The following 4 treatment groups will be set up: ASP015K 100 mg group, ASP015K 150 mg group, placebo group, and reference group.

The dose for each treatment group is shown in the table below. Two tablets of the drug described in the table below will be administered QD. The administration period will be 52 weeks. At Week 12, subjects in the placebo group will be switched to receiving either ASP015K at a dose of 100 mg or ASP015K at a dose of 150 mg under blind conditions. The dose of ASP015K to be administered to the placebo group from Week 12 will be determined in advance at baseline and will be continued until Week 52.

For the reference group, open-label etanercept will be administered for 52 weeks.

Table Treatment Periods and Doses by Treatment Period (Administered Drug) in Study 015K-CL-RAJ3

	Baseline–Week 12 ¹⁾	Week 12–Week 52
Placebo group	ASP015K placebo (ASP015K tablet 100 mg placebo and ASP015K tablet 150 mg placebo)	100 mg/day as ASP015K (ASP015K tablet 100 mg and ASP015K tablet 150 mg placebo)
		150 mg/day as ASP015K (ASP015K tablet 100 mg placebo and ASP015K tablet 150 mg)
ASP015K 100 mg group	100 mg/day as ASP015K (ASP015K tablet 100 mg and ASP015K tablet 150 mg placebo)	
ASP015K 150 mg group	150 mg/day as ASP015K (ASP015K tablet 100 mg placebo and ASP015K tablet 150 mg)	
Reference group	Etanercept 50 mg/week (the last dose will be given at Week 51.)	

1) At Week 12, subjects in the placebo group will be assigned to receiving either ASP015K 100 mg or ASP015K 150 mg. Subjects will continue receiving the assigned dose thereafter.

(2) Mode of administration

[ASP015K 100 mg, ASP015K 150 mg, and placebo groups]

The assigned study drug will be orally administered to subjects under double-blind conditions QD after breakfast. The baseline dose should be given at each study center on the day of the baseline visit after all assessments and tests are completed.

Doses on the day of scheduled visits during treatment with the study drug or reference drug should be given on the day of the visit after all assessments and tests are completed, except for blood sampling for the assessment of post-dose concentrations.

- CONFIDENTIAL -

[Reference group]

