4 SAMPLE SIZE

One hundred subjects per group will receive the study drug and 200 subjects the reference drug (a total of 500 subjects).

[Rationale for the sample size]

Based on 015K-CL-RAJ1 result and efficacy result from other RA drugs [XELJANZ[®], tablet, 5 mg, CTD (2013)] [CIMZIA, sc, 200 mg, Syringe, CTD (2012)], 62 subjects per group will provide 90% power to detect a difference assumed in the Step 2 in the closed testing procedure (described in Section 7.4.1.1 Primary Analysis) under the following assumptions. In addition, it is assumed that ACR20 response rate of each country (Japan, Korea and Taiwan) is similar.

- ACR20 response rate at Week 12 in the placebo group: 25%
- ACR20 response rate at Week 12 in the ASP015K 100 mg group: 54.5%

- ACR20 response rate at Week 12 in the ASP015K 150 mg group: 65.5%
- Two-sided significance level of 0.05

On the other hand, according to the Extent of Population Exposure to Assess Clinical Safety for Drugs Intended for Long-term Treatment of Non-life-threatening Conditions (PAB/PCD Notification No.592, dated 24 May 1995), ("the long-term treatment guideline"), a sample size of 300-600 subjects under long-term treatment (6 months) is adequate to observe delayed adverse events at a reasonable frequency (generally, 0.5% to 5%) and to observe whether there is an increase in high-frequency adverse events during the later stage of treatment. For treatment lasting 1 year, 100 subjects is acceptable. It is also described in "Guidelines on methodology for clinical assessment of antirheumatic drugs" (PFSB/ELD Notification No. 0217001, dated 17 February 2006) that 100 subjects for 1 year are necessary.

Therefore, to collect data for 300 subjects for 6 month period, and for 100 subjects for 1 year period in both ASP015K 100 mg and 150 mg groups among 015K-CL-RAJ2/RAJ3/RAJ4 studies as long-term treatment data, approximately 80 subjects per treatment group (400 subjects in total) as a target are necessary to be enrolled in Japan. In addition, the target sample size for Taiwan is set at 10 subjects per treatment group (50 subjects in total) as a target in consideration of the requirement of regulatory authority in Taiwan (10% or more Taiwan subjects) and target sample size for Korea is also set at 10 subjects per treatment group (50 subjects in total) as a target. Therefore, the target sample size per treatment group is set at 100 subjects in total for 3 regions.

[Rationale for the sample size for the reference group]

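### The time-to-first-response analysis takes non-responders out of the risk set too early, so its Kaplan-Meier curves overstate cumulative response in every arm

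*SAP*

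**What the plan says.** SAP section 7.4.1.6 analyses time to first ACR20-CRP response over the first 12 weeks, with Kaplan-Meier plots for all groups and a stratified log-rank test and Cox model for each dose against placebo. Section 7.4.2 applies the method to six more endpoints, so all seven listed in section 6.1.2.3 are covered.

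- **Discontinued without response.** The subject "will be censored at the date of early discontinuation".
- **Completed without response.** The subject "will be censored at one day before the dosing at Week 12 day up to Day 92".
- **Event.** The first response at any assessment, dated by the latest of its component assessments. "The definition of event is the same as the definition of the binary response".
- **Visit-day dosing.** Protocol section 5.1.1 says that doses on visit days "should be given on the day of the visit after all assessments and tests are completed", apart from the post-dose concentration sample. A Week 12 response is therefore dated on the Week 12 dosing day, one day after a completer without response has been censored.

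No competing-event estimate and no sensitivity analysis is planned for time to response. Section 7.4.2 sends the reader to 7.4.1.5 for the method, but 7.4.1.5 is the covariate-imbalance analysis; the method is in 7.4.1.6.

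**The concern.** Censoring says that the subject would have gone on to respond at the same rate as those still under observation. Neither rule fits that.

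For discontinuations, Protocol section 3.4 (criterion 2) withdraws a subject when treatment is judged insufficiently effective. SAP section 7.11.5 then drops efficacy data more than 2 days after the last study-drug dose (9 days for the reference drug). Someone who leaves without response has almost no chance of a later analysable response, so leaving acts as a competing event. The earlier study 015K-CL-RAJ1 points the same way: of its AE discontinuations, "The most common reason was rheumatoid arthritis aggravated (21/32").

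For completers, the problem is mechanical. Those who fail at Week 12 leave the risk set the day before those who succeed at the same visit are counted.

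At stake is the reading of seven sets of curves as probabilities of response. The binary ACR20 endpoint keeps discontinued subjects in the denominator through LOCF and has several missing-data sensitivity analyses; the time-to-event version has neither.

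**Working it through.** **Plan's own figures.** The documents give no figure for this analysis and no expected Week 12 dropout. The planning figure of 62 per group (25% against 54.5%, 90% power, two-sided 0.05) comes out at 63 with a continuity-corrected two-proportion formula and 56 without, so I take the planning rates as they stand.

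**Inputs.**

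| | Placebo | 100 mg | 150 mg | Source |
|---|---|---|---|---|
| Ever-response proportion, p | 25% | 54.5% | 65.5% | SAP section 4 (Week 12 rates used as a stand-in) |
| Discontinued without response, d | 17.9% | 10.9% | 6.9% | Protocol 1.3, RAJ1 AE discontinuations |

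Using d as Week 12 dropout, treating all of it as non-response, its timing, and the split of first responses over Days 29, 57 and 85 are my assumptions.

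**Discontinuation rule alone.** Completers are held to the end of the window. At each visit the survival factor is 1 − (responders at the visit) / (number still at risk). With responses and dropouts in equal thirds, per 100 placebo subjects 5.97 leave before each visit and 8.33 respond at it:

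- Day 29: 1 − 8.33/94.03 = 0.911
- Day 57: 1 − 8.33/79.73 = 0.895
- Day 85: 1 − 8.33/65.43 = 0.873
- 1 − KM = 1 − 0.712 = 28.8%, against 25%

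The same steps give 59.8% for 100 mg and 69.5% for 150 mg. If everyone leaves before Day 29, 1 − KM = p/(1 − d), which is the maximum: 25/82.1 = 30.5%, 54.5/89.1 = 61.2%, 65.5/93.1 = 70.4%. If all leave between Days 57 and 85 and responses come early (50/30/20), the results are 26.4%, 57.1% and 67.7%. The excess is thus +1.4 to +5.5 points on placebo, +2.6 to +6.7 on 100 mg and +2.2 to +4.9 on 150 mg. It is near zero if few leave before the last assessment. The difference from placebo goes from 29.5 to 30.7–31.1 points for 100 mg, and from 40.5 to 39.9–41.3 for 150 mg.

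**Both rules, all visits on nominal days.** Non-responding placebo completers number 100 − 25 − 17.9 = 57.1 per 100, and all are censored on Day 84. On Day 85 only the Week 12 responders remain, so the factor is 1 − 8.33/8.33 = 0 and the curve reaches 100%. The same happens in the active arms, whatever the true rate. Week 12 responses also add nothing to the log-rank test then, because everyone at risk has the event.

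**Both rules, visits spread over ±7 days.** Simulation: 100 per arm, 1,000 runs, first responses split 35/35/30 over the three visits, dropout uniform over Days 2–84, unstratified log-rank test.

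| Censoring of non-responders | Mean 1 − KM: placebo / 100 mg / 150 mg | Mean Z: 100 mg / 150 mg |
|---|---|---|
| As written | 67.6 / 93.3 / 96.8% | 3.78 / 5.04 |
| Completers on the Week 12 visit day; discontinuations as written | 46.1 / 80.8 / 88.7% | 3.89 / 5.18 |
| Completers to Day 92; discontinuations as written | 28.8 / 59.2 / 69.5% | 4.02 / 5.43 |
| Discontinuations to Day 92; completers as written | 31.9 / 65.1 / 78.0% | 4.09 / 5.67 |
| All to Day 92 | 25.2 / 54.1 / 65.6% | 4.17 / 5.75 |

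Only the last row recovers the input rates, within simulation error. Power for 100 mg is 97.5% in the first row and 98.8% in the last; for 150 mg it is 100% throughout.

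**The case against.** Several objections stand.

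- **The 21 of 32 is narrow evidence.** A reader might infer that most early withdrawals in this trial will be for worsening RA. The documents do not say so. The figure covers AE discontinuations only, in another study, pooled over five arms. No total by reason is given, and no figure for this trial. Protocol 2.2.2 describes RAJ1 as single-agent therapy, and its placebo ACR20 rate was 10.7% (Protocol 1.2.4), against the 25% planned here.
- **Cause-specific analysis is legitimate.** Censoring at a competing event is the usual way to estimate a cause-specific hazard. Only reading 1 − KM as a probability is wrong, so nothing here requires the log-rank test or Cox model to be replaced.
- **Withdrawal is reported elsewhere.** SAP section 7.2.1 plans a Kaplan-Meier plot of withdrawal to Day 92 and a test of withdrawal for lack of efficacy.
- **Rare endpoints move less under the discontinuation rule.** For an assumed 5% event rate and 17.9% dropout, the most it can add is 5/0.821 − 5 = 1.1 points.

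One defence of the completer rule does not hold. Censoring before the Week 12 dose looks meant to keep time after the placebo switch out of the analysis. But the visit-day assessments precede the dose, so counting them brings in no switched treatment.

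**Conclusion.** The curves overstate cumulative first response in every arm. The discontinuation rule contributes roughly 1 to 7 points under the stated assumptions. The completer rule is the larger fault: with both in force, arms of 100 average about 68%, 93% and 97%, and correcting discontinuations alone still leaves about 32%, 65% and 78%. The sizes depend on borrowed dropout rates and on assumed timing. The direction does not, provided that some non-responders leave before the last responses are counted.

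Two stronger readings are not supported. First, the bias does not favour the drug. The discontinuation rule moves the treatment difference by less than 2 points and lowers the log-rank statistic slightly. Both rules together shrink the displayed difference, to about 26 points for 100 mg and 29 for 150 mg. Second, these rules are not the only reason why the curves will differ from the ACR20 rates. First response at any visit is a different quantity from response at Week 12/ET: a subject who responds and then loses response counts in one and not the other, and would still do so after correction.

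These analyses are supportive. The primary analysis is not affected.

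**What to change.** In SAP section 7.4.1.6, and through it for all seven endpoints:

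1. For the curves, hold every non-responder, discontinued or completing, at risk as a non-responder to Day 92. Equivalently, report cumulative incidence with discontinuation as a competing event and completers held to Day 92. Label the curve as first response and note that it will not equal ACR20 at Week 12/ET.
2. The log-rank test and Cox model may keep censoring at discontinuation, described as cause-specific analyses. A completer's censoring date must not precede the Week 12 assessment; Day 92, as for the curves, is simplest.
3. Keep the curve with censoring at discontinuation as a sensitivity analysis, with completers held to Day 92.
4. Correct the reference in section 7.4.2 from 7.4.1.5 to 7.4.1.6.

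The cost is SAP wording, a changed censoring date and one extra analysis, with no new data. Displayed response probabilities will be lower: slightly so from the discontinuation change, and by much more where the completer rule would have been applied literally.
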